**d. Sample size calculation**

An 8.0 difference in the overall score in the QoR-15 questionnaire on postoperative day 7 is considered a minimal clinically relevant difference (16) with standard deviation of 19.1 (17). Group sample sizes of 91 patients achieve 80% power to detect a difference of -8.0 with a significance level (alpha) of 0,05 using a two-sided two-sample t-test. *Sample Size calculation is performed with PASS 2021 Power Analysis and Sample Size Software (2021). NCSS, LLC. Kaysville, Utah, USA, [ncss.com/software/pass](http://ncss.com/software/pass).* We plan to include 20% extra patients to adjust for dropout or incomplete data. Total sample will be 230 subjects divided into two groups.

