non-steroid inflammatory drug (NSAID), metoclopramide, pantoprazole and if they underwent a surgical procedure with intermediate risk for complications, they also receive tramadol or opioids.

In addition to standard care as delineated above, patients in the intervention group (remote monitoring after discharge) will have the monitoring application installed on their personal smartphone. Once they are back home, they can start recording pain and nausea and may ask questions about their recovery within the application. Once a day patients receive a push notification to record pain and nausea. The application is operational up to 7 days post discharge. After this period the application is disconnected from the Thuismeten (Luscii) © server.

In case of recording unbearable pain and nausea or asking a question and being in need for help or assistance, an anaesthesia medical assistant will contact these patients during office hours from 08:00 to 16:30 by using the applications' messaging service or by telephone. First the medical assistant will perform an initial triage of the patients in need, subsequently pain and nausea reports and additional questions that appear as an alert in the electronic back office systems of Thuismeten (Luscii) © will be addressed. The alerts are set to the in-app question 'do you want something to be done about your pain or nausea?' or an increase of 3 points numerical rating scale (NRS) for pain and additional questions asked in the apps messaging service. During triage, the medical assistant will follow a protocolled workflow to assess actions to be taken (APPENDIX II triage workflow, in Dutch). If contacting the patient by telephone is necessary, the medical assistant will use a call script to assess patients' pain, nausea and physical status (APPENDIX III, call script, in Dutch). The medical assistant will often give appropriate feedback or advice via message or telephone. In case of a possible medical alert or a necessary medication adjustment, the medical assistant will consult the anaesthetist, trainee nurse specialist or physician assistant responsible for remote postoperative pain care.

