### **iii. Other study parameters (if applicable)**

The following patient baseline characteristics are collected: age, sex, smoking status, body mass index, ASA classification, PONV score, preoperative NRS, PONV prophylaxis, previous surgical or anaesthesia related complications, history of (chronic) pain, history of motion sickness, surgical specialism, surgical procedure and classification (e.g. laparoscopic cholecystectomy, minor), anaesthesiology technique (i.e. general or spinal anaesthesia), surgery duration, intraoperative medication, PONV and NRS for pain at recovery ward, PONV and NRS for pain at day care ward, duration of admission

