### a. Primary study parameter(s)

The primary outcome, QoR-15 at day 1, 4 and 7, will be compared among patients randomized to either the intervention and control group, using Student's t-test or a nonparametric Mann Whitney U test.

Mixed effects linear regression models will be conducted to investigate the effect of the smartphone app on QoR-15 over the first week post discharge as a function of the randomization assignment (i.e. intervention vs control), time (i.e. measurements before surgery, and at day 1, 4 and 7 post discharge), and their interaction term. Random effects, i.e. random intercept, will be fitted per individual to account for clustering effects. To adjust for practice variation between the participating hospitals, the factor hospital will be added as fixed effect to the mixed model. In addition, we will perform a sensitivity analysis if the results of the mixed model analysis indicate for bias.

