### b. Secondary study parameter(s)

Postoperative pain on post discharge day 1, 4 and 7: Mean, Standard Deviation, Mixed effects linear regression models will be conducted to investigate the effect of the smartphone app on postoperative pain over the first week post discharge as a function of the randomization assignment (i.e. intervention vs control), time (i.e. measurements before surgery, and at day 1, 4 and 7 post discharge), and their interaction term. Random effects, i.e. random intercept, will be fitted per individual to account for clustering effects

Post discharge Nausea and Vomiting (PDNV) on post discharge day 1, 4 and 7: Mean, Standard Deviation and Mixed effects linear regression models will be conducted to investigate the effect of the smartphone app on PDNV over the first week post discharge as a function of the randomization assignment (i.e. intervention vs control), time (i.e. measurements before surgery, and at day 1, 4 and 7 post discharge), and their interaction

term. Random effects, i.e. random intercept, will be fitted per individual to account for clustering effects

Medication Dosage and usage measured in morphine equivalents on post discharge day 1, 4 and 7: Mean, Standard Deviation and Mixed effects linear regression models will be conducted to investigate the effect of the smartphone app on medication dosage and usage over the first week post discharge as a function of the randomization assignment (i.e. intervention vs control), time (i.e. measurements before surgery, and at day 1, 4 and 7 post discharge), and their interaction term. Random effects, i.e. random intercept, will be fitted per individual to account for clustering effects

Difference in the number contacts with the hospital, general practitioner or emergency department (on day 7 post discharge): Mean and Standard Deviation and two sample-t-test (in case of non-normally distributed data we will report on medians and interquartile ranges and differences will be tested using the Mann-Whitney U test)

Difference in the number of surgical complications assessed according to the Clavien Dindo classification of surgical complications (on day 7 post discharge): Mean, Standard Deviation and two sample-t-test (in case of not normally distributed data we will use the Mann-Whitney U test)

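### Specialty and procedure class are recorded but enter no planned analysis: a missed, inexpensive gain in precision for the day-7 QoR-15 comparison, not an error

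*Combined protocol and SAP*

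**What the plan says.** **Population.** The inclusion criteria admit seven surgical specialties. The introduction speaks of minor and intermediate surgery, and section 4.a separates discharge medication by risk: "if they underwent a surgical procedure with intermediate risk for complications, they also receive tramadol or opioids".

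**Data collected.** Section 7.a.iii lists among the baseline characteristics "surgical specialism, surgical procedure and classification (e.g. laparoscopic cholecystectomy, minor".

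**Randomisation.** Section 7.b uses permuted blocks of four stratified by hospital, and by nothing else.

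**Analysis.** Section 9.a has two parts.
- QoR-15 is compared between arms by t-test or Mann-Whitney test, with no covariate.
- A mixed model contains arm, time (including the pre-surgery score), their interaction and a random intercept per patient. For covariates, "To adjust for practice variation between the participating hospitals, the factor hospital will be added as fixed effect to the mixed model".

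The secondary mixed models in section 9.b are set up, for pain, "to investigate the effect of the smartphone app on postoperative pain over the first week post discharge as a function of the randomization assignment", with time and the interaction. They name no covariate, not even hospital. Section 9.a also allows a sensitivity analysis if the mixed model points to bias, but states no trigger and no covariates.

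**Sample size.** The calculation rests on the unadjusted test: "Group sample sizes of 91 patients" are said to "achieve 80% power to detect a difference of -8.0 with a significance level (alpha) of 0,05 using a two-sided two-sample t-test".

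**The concern.** Operations from seven specialties and of different severity plausibly differ in recovery at day 7. If they do, that variation stays in the residual of the planned comparison and widens the interval for the treatment difference. The pre-surgery QoR-15, which the mixed model does use, reflects stable differences between patients. It cannot carry the effect of an operation that has not yet taken place.

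With hospital as the only stratification factor, procedure mix can also differ between arms by chance. No planned analysis would correct the estimate for that. Medication use in morphine equivalents is the outcome most exposed, because by section 4.a the risk of the procedure determines who leaves with tramadol or an opioid.

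At stake is precision obtainable from data already on the collection list, and the chance to fix the adjustment before outcomes are seen and not after an imbalance has been noticed.

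**Working it through.** **Inputs from section 3, sample size calculation.** Difference 8.0 ("An 8.0 difference in the overall score in the QoR-15 questionnaire on postoperative day 7 is considered a minimal clinically relevant difference"), SD 19.1 ("with standard deviation of 19.1"), 91 per arm, two-sided alpha 0.05.

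**Inputs not in the documents (assumptions).**
- R², the share of day-7 QoR-15 variance explained by specialty and class: 0.05 to 0.20.
- Two classes (minor, intermediate), so seven covariates: 6 for specialty and 1 for class.
- For the imbalance check: 30% intermediate procedures (range 20% to 40%) and a day-7 gap between classes of 8 to 15 points.

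**1. The plan's own figure.** SE = 19.1 × √(2/91) = 2.83. The noncentral t distribution with 180 df gives power 80.2% at 91 per arm, so 91 reproduces. For dropout, 91/0.8 = 113.75, or 114 per arm and 228 in total, close to the stated 230.

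**2. Day-7 model with seven covariates.** Adjusted SE = 2.83 × √(1 − R²) × √(1 + 7/172). The last factor is the average price of estimating seven coefficients: 182 − 9 − 1 = 172, and 1 + 7/172 = 1.0407. Hospital terms are left out on both sides of the comparison.

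| R² | SE, no penalty | SE, net | Power, net |
|---|---|---|---|
| 0 (unadjusted) | 2.83 | – | 80.2% |
| 0.02 | 2.80 | 2.86 | 79.4% |
| 0.05 | 2.76 | 2.82 | 80.7% |
| 0.10 | 2.69 | 2.74 | 82.7% |
| 0.15 | 2.61 | 2.66 | 84.8% |
| 0.20 | 2.53 | 2.58 | 86.9% |

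Break-even: 1 − 1/1.0407 = 0.039. Below an R² of about 0.04, seven covariates cost as much as they return, or slightly more.

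**3. Class alone (one covariate).** The factor is 1 + 1/178 = 1.0056. If class by itself explained 5% to 20%, power would be 82.0% to 88.0%.

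**4. Chance imbalance in class.** At 30% prevalence, the SD of the between-arm difference in proportions is √(0.3 × 0.7 × 2/91) = 0.068, so the 95% range is ±13 percentage points. The shift in the day-7 difference is
- gap 15: 1.96 × 0.068 × 15 = ±2.0 points;
- gap 8: 1.96 × 0.068 × 8 = ±1.1 points.

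Over prevalences of 20% to 40%, the shift runs from ±0.9 (20%, gap 8) to ±2.1 (40%, gap 15).

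**5. Steps 2 and 4 measure one quantity.** With a gap of 15, the variance of the shift is (0.068 × 15)² = 1.04. The variance of the unadjusted difference is 2.83² = 8.02, and 1.04/8.02 = 13%. The R² of class under the same assumptions is 0.21 × 225/19.1² = 13%. With a gap of 8 both are 3.7%.

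**6. Mixed model.** A small simulation of the planned model (182 patients, complete data, within-patient correlation 0.5 assumed, 40 runs per setting, specialty only, acting only after surgery) gave these mean SEs for the day-7 group-by-time term:

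| R² | Hospital only | + specialty | + specialty × time |
|---|---|---|---|
| 0.10 | 2.796 | 2.796 | 2.763 |
| 0.20 | 2.771 | 2.771 | 2.670 |

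A main effect alone leaves this term unchanged. With the interaction the SE falls by 1.2% and 3.6%. Seven terms with four time points take 7 + 7 × 3 = 28 coefficients.

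**The case against.** The strongest reply is that nothing is broken. Stratifying by hospital and putting hospital in the QoR-15 mixed model is coherent. Randomisation keeps the estimate unbiased on average, the type I error does not need further covariates, and the 80% power reproduces without them. Adjustment for unstratified prognostic factors is optional. All of this stands, and it sets the weight of the point.

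Four stronger readings are tempting, and the documents do not support them.

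- *Imbalance is a second harm on top of lost precision.* Step 5 shows that it is the same variance seen another way, and the planned confidence interval already allows for it. Adjustment helps conditionally, in the sample actually drawn.
- *The protocol itself treats procedure class as decisive for recovery.* Section 4.a ties risk of complications to discharge medication and says nothing about QoR-15. That class predicts day-7 QoR-15 is plausible but assumed.
- *The whole analysis adjusts for hospital only.* Hospital is in the QoR-15 mixed model, which also carries the pre-surgery score. The direct comparison adjusts for nothing, and the secondary models name no covariate.
- *The gain is free.* Without the covariate penalty, power would read 82.2% to 88.1% for R² of 0.05 to 0.20. Net of it the range is 80.7% to 86.9%, with a possible slight loss at low R².

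One practical objection also stands. Section 7.a.iii does not say that the classification is the planned one, and its list includes items known only later, such as surgery duration and pain scores on the recovery ward. Section 7.c has baseline characteristics recorded around randomisation, which cannot hold for the whole list. The scheduled specialty is an eligibility criterion and so is known beforehand; the class is not shown to be.

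**Conclusion.** The point holds as a missed gain in precision and in conditional protection against chance imbalance. It is not a flaw in validity: a reader might infer that the primary result would be biased or the trial underpowered, and neither follows.

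The size depends on an R² that the documents do not give. Over 0.05 to 0.20 the net gain is between half a percentage point and just under seven points of power, and the reduction in SE is between about 0.5% (2.83 to 2.82) and 9% (2.83 to 2.58). A chance imbalance in class would move the day-7 difference by up to ±1.1 to ±2.0 points in 95% of trials at 30% intermediate procedures, against a target of 8.0.

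The undefined sensitivity analysis in section 9.a does not meet the need, since a covariate chosen after an imbalance is seen would be a post-hoc choice. Weight: cheap improvement, minor to moderate.

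**What to change.** - **Section 9.a, direct comparison.** Prespecify the day-7 QoR-15 comparison as a linear model with arm, hospital, procedure class (minor/intermediate) and specialty. State in advance how small specialties are pooled. This replaces the choice between t-test and Mann-Whitney for the main estimate, since the Mann-Whitney test takes no covariates. If the sponsor expects specialty to add little beyond class, class alone is a reasonable choice and costs one degree of freedom.
- **Definition.** Use specialty and class as scheduled before randomisation, not as performed. The sponsor should confirm that the eCRF holds the planned class with that timing; if it does not, a field has to be added.
- **Mixed models in sections 9.a and 9.b.** If class is included, enter it with its interaction with time. A main effect alone does nothing for the group-by-time term.

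**Cost.** A few lines of analysis text, written before outcomes are seen, and up to seven degrees of freedom at day 7. Interacting all seven terms with time would take 28 coefficients, which is a reason to limit the mixed models to class. The sample size need not change.

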### b. Secondary study parameter(s)

Postoperative pain on post discharge day 1, 4 and 7: Mean, Standard Deviation, Mixed effects linear regression models will be conducted to investigate the effect of the smartphone app on postoperative pain over the first week post discharge as a function of the randomization assignment (i.e. intervention vs control), time (i.e. measurements before surgery, and at day 1, 4 and 7 post discharge), and their interaction term. Random effects, i.e. random intercept, will be fitted per individual to account for clustering effects

Post discharge Nausea and Vomiting (PDNV) on post discharge day 1, 4 and 7: Mean, Standard Deviation and Mixed effects linear regression models will be conducted to investigate the effect of the smartphone app on PDNV over the first week post discharge as a function of the randomization assignment (i.e. intervention vs control), time (i.e. measurements before surgery, and at day 1, 4 and 7 post discharge), and their interaction

term. Random effects, i.e. random intercept, will be fitted per individual to account for clustering effects

Medication Dosage and usage measured in morphine equivalents on post discharge day 1, 4 and 7: Mean, Standard Deviation and Mixed effects linear regression models will be conducted to investigate the effect of the smartphone app on medication dosage and usage over the first week post discharge as a function of the randomization assignment (i.e. intervention vs control), time (i.e. measurements before surgery, and at day 1, 4 and 7 post discharge), and their interaction term. Random effects, i.e. random intercept, will be fitted per individual to account for clustering effects

Difference in the number contacts with the hospital, general practitioner or emergency department (on day 7 post discharge): Mean and Standard Deviation and two sample-t-test (in case of non-normally distributed data we will report on medians and interquartile ranges and differences will be tested using the Mann-Whitney U test)

Difference in the number of surgical complications assessed according to the Clavien Dindo classification of surgical complications (on day 7 post discharge): Mean, Standard Deviation and two sample-t-test (in case of not normally distributed data we will use the Mann-Whitney U test)

Difference in the number of readmissions emergency department (on day 7 post discharge): Mean, Standard Deviation and two sample-t-test (in case of not normally distributed data we will use the Mann-Whitney U test)

Satisfaction (on day 7 post discharge): Median, Interquartile Range and  $\chi^2$  tests for equal proportion.

General evaluations regarding provided care after discharge (on day 7 post discharge): Median, Interquartile Range and  $\chi^2$  tests for equal proportion.

Experienced quality of communication: Data collection and analysis progression were discussed during regular meetings with researchers. A thematic framework will be used to analyze the qualitative data. First, the audio recordings of the interviews will be transcribed verbatim in Dutch. After familiarization with the data, the transcripts are coded. After coding, overarching themes and patterns are identified and labelled within each concept.

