#### ii. Secondary study parameters/endpoints (if applicable)

Quality of recovery measured with the quality of recovery questionnaire-15 (QoR-15) (16, 24) at post discharge day at post discharge day 1, 4 and 7.

Postoperative Pain: Experienced postoperative pain (POP) measured with (in-app) NRS for Pain (25) (combined with 11 faces scale) measured at day 1, 4 and 7 post discharge.

Post discharge nausea and vomiting: Experienced post discharge nausea and vomiting (PDNV) measured with the Myles' PDNV assessment scale (21) between intervention and non-intervention group. Measured at day 1, 4 and 7 post discharge.

Medication Dosage and Use: the total dosage of administered analgesics will be assessed during hospital stay and recorded in the medical record. The total dosage of administered analgesics at home after discharge will be assessed by asking patients to indicate which pain medication they have been using. Measured at day 1, 4 and 7 post discharge.

The number of contacts with the hospital, general practitioner or emergency department. All types of contacts (e.g. physically, e-mail, telephone) will be assessed by reviewing the PDMS for registered contacts and by asking the patients to indicate the number of contacts.

Measured at day 1, 4 and 7 post discharge.

The number of surgical complications assessed according to the Clavien Dindo classification of surgical complications (26, 27) will be assessed by reviewing the PDMS and by asking the patients to indicate the number of complications. Measured at day 1, 4 and 7 post discharge.

The number of readmissions. A readmission is defined as an admission to hospital or emergency department for medical care or observation regarding their surgical intervention. Readmissions will be assessed by reviewing the PDMS and by asking the patient to indicate the number of readmissions. Measured at day 1, 4 and 7 post discharge.

Satisfaction: Patients' satisfaction with the provided care will be assessed using a 1-item self-created VAS scale ('not at all to very much', 0-10 range). Satisfaction will be measured at day 1, 4 and 7 post discharge.

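### The pain model gives the preoperative NRS its own free arm difference, does not adjust for it and names no contrast; adjusting for it and naming the contrast would gain precision at no cost

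*Combined protocol and SAP*

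**What the plan says.** Section 9.b gives the pain analysis as a mean, an SD and a mixed-effects linear model with arm, time and arm-by-time. The stated target is the "effect of the smartphone app on postoperative pain over the first week post discharge". Time is defined as "time (i.e. measurements before surgery, and at day 1, 4 and 7 post discharge), and their interaction term", so it has four levels, the first of them before surgery. The only random effect is an intercept: "Random effects, i.e. random intercept, will be fitted per individual to account for clustering effects".

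Section 7.a.ii defines the pain endpoint after discharge only: an NRS "combined with 11 faces scale) measured at day 1, 4 and 7 post discharge". Section 7.a.iii lists the preoperative value among the baseline characteristics: "ASA classification, PONV score, preoperative NRS, PONV prophylaxis".

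No section enters the preoperative NRS as a covariate or sets the arms equal before surgery. None says which term or contrast of the model is the effect on pain. For pain, unlike the QoR-15 in section 9.a, no separate two-group test is planned, so this model is the only inferential analysis.

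**The concern.** Before surgery the app cannot have changed pain, and randomisation makes the expected arm difference zero. A model that estimates a free arm difference at that level makes no use of this knowledge. What it then delivers depends on the line of output that is read:

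- The arm-by-time term compares changes from preoperative pain, and so carries the measurement noise of two occasions.
- The arm difference at a given day ignores preoperative pain, although it is collected.
- The arm coefficient, if the preoperative level is the reference, is the preoperative difference, which is zero in expectation.

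Because no contrast is named, the choice among these could be made after the data are seen. Pain is a named secondary objective, and a real benefit could be missed for want of precision that the trial's own data could supply.

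**Working it through.** **The plan's own figure.** The sample size section is about the primary endpoint: "An 8.0 difference in the overall score in the QoR-15 questionnaire on postoperative day 7", SD 19.1, two-sided alpha 0.05, 80% power. A two-sample t-test needs 90.45, hence 91 per arm (power 80.2%). Allowing for 20% dropout, 182/0.8 = 227.5, so 228, consistent with the stated 230. The figure reproduces. There is no corresponding figure for pain.

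**Inputs for pain.**
- From the documents: 230 patients and 20% dropout, so 230 × 0.8 / 2 = 92 per arm (1:1 assumed); a random intercept, which implies one correlation r between any two visits.
- Assumed, because the documents do not give them: SD 2.0 NRS points at every visit, true effect 0.8 points, r from 0.2 to 0.8.

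**Standard errors at one day.**
- Unadjusted day contrast: SE = 2.0 × sqrt(2/92) = 0.295.
- Change from baseline (arm-by-time): 0.295 × sqrt(2(1−r)).
- Covariate adjustment: 0.295 × sqrt(1−r²).
- Change relative to adjustment: sqrt(2(1−r)/(1−r²)) = sqrt(2/(1+r)), above 1 for every r below 1.
- Change relative to unadjusted: sqrt(2(1−r)), above 1 only for r below 0.5.

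Power is Φ(0.8/SE − 1.96):

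| r | Unadjusted day contrast | Change contrast | Covariate-adjusted | SE ratio, change to adjusted |
|---|---|---|---|---|
| 0.2 | 77% | 57% | 79% | 1.29 |
| 0.3 | 77% | 63% | 81% | 1.24 |
| 0.5 | 77% | 77% | 88% | 1.15 |
| 0.7 | 77% | 94% | 97% | 1.08 |
| 0.8 | 77% | 99% | 99% | 1.05 |

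**Average over days 1, 4 and 7.** Here the assumptions are an effect of 0.3 SD on all three days and 91 per arm. The variances, in units of the visit variance, are (1+2r)/3 unadjusted, (1+2r)/3 + 1 − 2r for change and (1+2r)/3 − r² adjusted.

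| r | Unadjusted | Change | Adjusted |
|---|---|---|---|
| 0.2 | 84% | 50% | 87% |
| 0.5 | 70% | 70% | 88% |
| 0.8 | 58% | 98% | 99% |

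**Simulation.** The planned four-level model was fitted to 150 data sets with 91 per arm, r = 0.4 and a true effect of 0.50 SD after discharge:
- Day-7 contrast: mean 0.51, empirical SE 0.144; identical to the raw day-7 difference.
- Day-7 interaction: mean 0.51, SE 0.163.
- Day 7 adjusted for the preoperative value: mean 0.51, SE 0.131.
- Arm coefficient with the preoperative level as reference: mean 0.00.
- Arm effect averaged over all four levels: mean 0.38, which is about (0 + 3 × 0.50)/4.

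The interaction-to-adjusted variance ratio is (0.163/0.131)² ≈ 1.5, against 2/(1+0.4) = 1.43 in theory.

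**The case against.** A reader might infer that the planned model dilutes the pain effect to three quarters of its size, or that its only alternative is a noisy change score. The documents do not support this. The 0.75 factor arises only if the arm effect is averaged over all four levels. The plan names no such average, and it would sit badly with an item headed by days 1, 4 and 7 and aimed at the first week after discharge. A day-specific contrast, or the average of the three post-discharge days, comes from the same model without dilution.

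A reader might also infer bias. Under randomisation the change contrast and the day contrasts are both unbiased; what differs is their precision. Nor is change always worse than ignoring baseline: at r = 0.5 the two are equal, and above it change is better. Nothing in the documents shows where r lies for this mix of specialties.

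Nor is keeping the preoperative value in the outcome vector an error in itself, since a model with a common preoperative mean does exactly that. The weakness is the unconstrained arm difference at that level.

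Finally, pain is a secondary endpoint without its own power calculation, and the planned two-group test of QoR-15 is untouched. On the mildest reading, the unadjusted day contrast, the loss is about 4 percentage points of power at r = 0.3 and 11 at r = 0.5 under the assumptions above.

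All of this stands and limits the point. It does not remove it: adjustment is more precise than either alternative for every r between 0 and 1, and the contrast is still unnamed.

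**Conclusion.** The point holds as a free gain in precision together with a missing definition of the reported effect. It does not show that the pain effect is diluted or biased.

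Its size depends on which contrast the analyst would have reported and on r. Relative to covariate adjustment, the change contrast has a standard error 24% larger at r = 0.3 and 5% larger at r = 0.8. For the unadjusted day contrast the order is reversed: its ratio is 1/sqrt(1−r²), so 5% larger at r = 0.3, 15% at 0.5 and 67% at 0.8. The power figures rest on the assumed SD, effect and r, on equal variances and on a common correlation across visits. That adjustment is the most precise of the three does not depend on the assumed SD or effect.

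**What to change.** In section 9.b, replace the pain model by either of these:

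1. Outcome at days 1, 4 and 7 only, with arm, time, arm-by-time, and the preoperative NRS and its interaction with time as covariates.
2. The four-level model, with both arms constrained to one common preoperative mean.

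In either case, state in advance that the reported effect is the arm difference at each day, or the average over days 1, 4 and 7.

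The cost is wording. The preoperative NRS is already collected, and no visit or patient is added. The one downside of option 1 is that a missing preoperative NRS must be imputed; option 2 handles it within the model.

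The QoR-15 mixed model in section 9.a uses the same definition of time. It can be changed in the same way, since the Summary provides for a preoperative QoR-15 in both groups.

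### For contacts, complications and readmissions, the plan's normality rule leads in practice to a Mann-Whitney p-value with no effect measure or confidence interval, although the objectives ask for a difference in number

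*Combined protocol and SAP*

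**What the plan says.** Section 2c lists, among the secondary objectives, the between-arm difference in the number of surgical complications, of readmissions and of contacts with hospital or general practitioner. Section 7a(ii) defines the three measures. Contacts cover every route (in person, e-mail, telephone), and readmissions include emergency department admissions related to the surgery.

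Section 9b sets the analyses, all at day 7 after discharge:

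- **Readmissions:** "Difference in the number of readmissions emergency department (on day 7 post discharge): Mean, Standard Deviation and two sample-t-test", with Mann-Whitney if the data are not normally distributed.
- **Complications:** the entry begins "Difference in the number of surgical complications assessed according to the Clavien Dindo classification" and has the same mean, SD, t-test and Mann-Whitney fallback.
- **Contacts:** mean, SD and t-test, but here the fallback also changes the summary: "in case of non-normally distributed data we will report on medians and interquartile ranges and differences will be tested" by Mann-Whitney.

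The opening of Section 9 says that distributions are judged from histograms and normality tests. For these three endpoints the plan names no effect measure, confidence interval, proportion of patients with an event, count model or tabulation by Clavien-Dindo grade. Hospital is a randomisation stratum (Section 7b) and a factor in the primary mixed model (Section 9a), but it does not enter these comparisons.

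**The concern.** The objectives are about size: how many more or fewer events occur with remote monitoring. A Mann-Whitney test does not estimate a difference in number. If the fallback is the branch that will be used, the plan commits the trial to a p-value for each count and leaves open what is reported beside it.

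This matters most for complications and readmissions. Section 8e provides for no DSMB and Section 6d expects no harm, so these are among the few comparisons between arms that bear on safety. The trial is sized for QoR-15 and not for these events, so non-significant results are likely whatever the truth. Without an interval, such a result can be read as no difference when the data are compatible with a sizeable difference in either direction.

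**Working it through.** **1. The plan's own figure.** The only stated size is for the primary endpoint: "Group sample sizes of 91 patients achieve 80% power to detect a difference of -8.0", with SD 19.1 and a "significance level (alpha) of 0,05 using a two-sided two-sample t-test". Noncentral t: power is 0.798 at 90 per group and 0.802 at 91, so 91 reproduces. With the 20% allowance, 91 / 0.8 = 113.75, or 114 per arm and 228 in total. The plan says "Total sample will be 230 subjects divided into two groups", which is 115 per arm if split equally. The checks below use 91 and 115 per arm.

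**2. Which branch will be used?** The plan names no particular normality test; Shapiro-Wilk at 0.05 is assumed. Poisson counts were simulated with means 0.02, 0.05, 0.1, 0.3, 0.5, 1, 2 and 3, with 1,000 samples at each mean for 91 and 115 per arm. Normality was rejected in 100% of samples that had any variation. The rule, applied as written, leads to Mann-Whitney for all three endpoints across this range.

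**3. How sparse are the counts?** The documents give no event rates, so a range is shown. Suppose each patient has an event with probability p (binomial, one arm):

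| p | Median 0 | 75th percentile 0, n = 91 | 75th percentile 0, n = 115 |
|---|---|---|---|
| 3-10% | about 100% | above 99.9% | above 99.9% |
| 15% | about 100% | 99.3% | 99.7% |
| 20% | about 100% | 87% | 90% |

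Up to about 15%, then, quartiles carry no information on complications or readmissions. Contacts are different. At a Poisson mean of 1, a single arm's median was 0 in under 1% of samples, and at means of 2 and 3 never. With overdispersion (negative binomial, mean 1, dispersion 1), both medians were 0 in about 25% of runs.

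**4. What each method would report.** Illustrative counts (assumed), 3/91 in arm A against 7/91 in arm B:

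- Wilson 95% limits: A 3.30% (1.13 to 9.25); B 7.69% (3.78 to 15.04).
- Risk difference A - B = 3.30 - 7.69 = -4.4 points.
- Newcombe lower limit: -4.40 - √[(3.30 - 1.13)² + (15.04 - 7.69)²] = -4.40 - 7.66 = -12.1.
- Newcombe upper limit: -4.40 + √[(9.25 - 3.30)² + (7.69 - 3.78)²] = -4.40 + 7.13 = +2.7.
- Mann-Whitney on the same data: p = 0.20, with no estimate.

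For 3/91 against 3/91 the half-width is √(2.17² + 5.95²) = 6.3, so the result is 0 (-6.3 to +6.3 points). Mann-Whitney gives p = 1.0, which hides that 6 points either way remain compatible with the data.

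**5. Is a non-significant result likely?** For 5% against 10% at 115 per arm, the pooled proportion is 0.075. SE under no difference = √(0.075 × 0.925 × 2/115) = 0.0347. SE under the alternative = √[(0.0475 + 0.09)/115] = 0.0346. Power = Φ[(0.05 - 1.96 × 0.0347)/0.0346] = Φ(-0.52), about 30%. Reaching 80% would need 435 per arm.

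**The case against.** The plan is not statistically invalid. In simulation the t-test held its type I error (3.9-5.4%), the 95% interval for the mean difference covered at 94-96%, and Mann-Whitney also held its level (4.0-5.3%). With at most one event per patient, the difference in means is the risk difference. For 3/91 against 7/91 the t-interval is -4.4 (-11.1 to +2.3), close to Newcombe. A reader might infer that the plan can yield no usable effect estimate at all. That does not hold for the t-test branch; the gap opens when the normality rule discards that branch.

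A reader might also infer that all three endpoints will be reported as identical zero medians. The documents do not support this. Medians and quartiles are the named fallback for contacts only. For complications and readmissions the fallback changes only the test, so on a literal reading the means stay and a crude difference can be worked out, though without an interval. Nor can contacts be taken as mostly zero: every e-mail, telephone call and visit counts, and Section 4a has staff messaging or telephoning intervention patients after alerts.

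On Clavien-Dindo, nothing says that grades will go unreported; the plan simply does not specify a tabulation. Finally, the endpoints are secondary, and the proposed intervals will be wide and will not exclude moderate harm. All of this stands. What it does not answer is that no effect measure or interval is specified on the branch the data will follow.

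**Conclusion.** The concern holds in a limited form. For contacts, complications and readmissions, the plan's own rule leads to Mann-Whitney at every count mean examined (0.02 to 3 per patient), and on that branch it names no effect measure or confidence interval for objectives that ask for a difference in number.

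The branch conclusion assumes a formal test such as Shapiro-Wilk and Poisson-like counts. The statement that most patients have no complication or readmission rests on an assumed rate of up to about 15% over 7 days. That is plausible for ASA I-III day-care patients discharged the same day, but the documents do not give a rate. No such assumption is made for contacts; for them only the missing effect measure and interval count. The QoR-15 conclusion and the sample size are unaffected.

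**What to change.** Amend Section 9b before the database is locked:

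- **Complications and readmissions:** replace the t-test/Mann-Whitney rule with the number and percentage of patients with at least one event in each arm, and the risk difference with a 95% CI (for example Newcombe).
- **Complications:** add a table by arm of the highest Clavien-Dindo grade per patient.
- **Contacts:** report a rate ratio with 95% CI from a negative binomial model with hospital as a factor, or the mean difference with a robust or bootstrap 95% CI, instead of switching to medians and Mann-Whitney.

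Newcombe and negative binomial are reasonable choices among several; what matters is that an effect measure and interval are fixed in advance. The cost is revised wording and a little more analysis, with no new data. The intervals will be wide, and the report should say so.
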